4.3 Pre-treatment Evaluation/Screening

- 4.3.1 MRI scan with and without contrast (at least 5mm resolution on T1 post-contrast imaging).
- 4.3.2 History and physical including a detailed neurologic exam.
- 4.3.3 Steroid and anti-convulsant doses must be documented.
- 4.3.4 Baseline MMSE.
- 4.3.5 Baseline neurocognitive function using the HVLT-R (memory).
- 4.3.6 Baseline neurocognitive function using MOS (self-report).
- 4.3.7 Baseline QOL assessment using FACT-Br.
- 4.3.8 Documentation of extent of systemic disease.
- 4.3.9 Pregnancy test in women of child bearing potential

4.4 Recruitment Plan

Patients with brain metastases who are referred to Emory Radiation Oncology for brain radiotherapy either in the setting of intact solid metastatic tumor(s) or after resection of the metastatic tumor(s) will be considered for this study. All Emory radiation oncology physicians will be made aware of the trial, including main objectives and patient eligibility. Once the trial is open to accrual it will be up to the primary radiation oncologist to screen patients for eligibility, explain the risk and benefits of trial participation, and inform patients of the alternative treatment options off of study. Copies of this study protocol and eligibility checklist (**Appendix E**), study consents (**Appendix F and G**) and initial assessment form (**Appendix H**) will be made available to all physicians in the radiation oncology department at Emory University Hospital and Emory University Hospital Midtown.

4.5 Informed Consent

Eligible patients will be informed of all options for brain radiotherapy, which may include whole brain radiation therapy, partial brain radiation therapy to the tumor/resection cavity only delivered with fractionated radiosurgery either on or off the this study, or a combination of the two. Risks and benefits of each option will be discussed and patients who elect to receive partial brain radiation therapy only will be offered participation in the trial and given a copy of the informed consent (**Appendix G**). Informed consent will be signed and witnessed after all patient questions have been

4.6 Criteria for patient to be considered off study

- 4.6.1 Patient death.
- 4.6.2 Patient undergoes whole brain radiation therapy. However, we will continue to follow the patient after whole brain radiation therapy to document whether there are any enhanced toxicities with the combination of the study treatment and whole brain radiotherapy.
- 4.6.3 Patient request to come off study.

5.0 STATISTICAL ANALYSIS

5.1 Study endpoints

- 5.1.1 Primary endpoints

1. MTD
2. Neurologic toxicity due to treatment
- 5.1.2 Secondary Endpoints
 1. Local Control
 2. Margin Control
 3. Distant brain control
 4. Freedom From Failure/Progression Free Survival
 5. Overall Survival
 6. Neurocognitive effects
 7. QOL outcomes

5.2 Sample size

Dose escalation on this study will be using EWOC design. There will be 3 patients per dose escalation and enrollment will be done sequentially. A **fixed sample size of 24 will be used.**

If a patient is not able to complete follow up to the toxicity assessment point of 4 months due to a toxicity judged not to be at least possibly related to therapy, then that patient will be replaced at the same dose level by the next patient enrolled into that cohort.

5.3 Statistical Analysis

5.3.1 Primary Analysis: The rate of toxicities at 4 months will be calculated with 95% confidence interval (CI).

5.3.2 Secondary Analysis:

5.3.2.1 The median time to local/distant brain progression will be calculated by Kaplan-Meier method with 95% CI. For a given time point, say 4 month, the rate of local/distant progression will be calculated with 95%CI.

5.3.2.2 The median of OS time with 95% CI will be calculated by Kaplan-Meier method.

5.3.2.3 Neurocognitive effect and QOL outcomes will be regressed over time using GEE model. The population change over time (slope) will be estimated with 95%CI.

5.3.3 Patient Stratification: All enrolled patients will proceed through dose escalation as a single cohort, however patients will be analyzed as separate strata, should enrollment allow it, based on the following criteria.

5.3.3.1 Intact brain metastasis versus resection cavity.

5.3.3.2 No previous cranial irradiation versus previous WBRT or other cranial irradiation.

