2.1.1 Maximum tolerated dose (MTD)

2.1.2 Dose limiting toxicity (DLT): any acute or late CNS toxicity with grade greater than or equal to 3 with attribution score greater than or equal to 3.

2.2 Secondary Endpoints:

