3.2 Enrollment/Randomization

This study will include 8 patient cohorts with 3 patients per cohort. The patients will be enrolled and treated following a Bayesian method permitting precise determination of the therapeutic working-dose while directly controlling the likelihood of an overdose. The method, known as Escalation with Overdose Control (EWOC), has been used to design phase I clinical trials at several cancer centers including the Fox Chase Cancer Center (PA), the Sylvester Comprehensive Cancer Center (FL), and the Winship Cancer Institute (GA) and pharmaceutical companies. EWOC was the first dose-finding procedure to directly incorporate the ethical constraint of minimizing the chance of treating patients at unacceptably high doses. Its defining property is that the expected proportion of patients treated at doses above the MTD is equal to a specified value α , the feasibility bound. This value is selected by the clinician and reflects his/her level of concern about overdosing.

The dose levels for the trial are summarized in Table 1. The dose for the first cohort of 3 patients in the trial will be the dose level 0, previous results indicating this to be a safe dose. The patient accrual will be suspended until the 4 month toxicity evaluation is completed for all previously enrolled patients. The dose for each subsequent cohort of 3 patients will be determined so that, on the basis of all available data and the target highest acceptable toxicity level of 25% DLT, the probability that it exceeds the MTD is equal to a pre-specified value α . In this trial, we set $\alpha = 0.25$ and increase α in small increments until $\alpha = 0.5$, this value being a compromise between the therapeutic aspect of the agent and its toxic side effects. The dose selected for every patient in the trial will be between the minimum dose of 27.5 Gy and the maximum allowable dose of 40 Gy. The trial will be terminated if 3 DLTs are observed in any cohort of 3 patients treated with the lowest dose level. The trial will stop after 24 patients have been enrolled and MTD will be estimated from one of the 6 specified dose levels listed in the Table 1. If no MTD is found because even the highest dose level is still considered under toxic, then the highest dose group will be considered the MTD and expanded to 12 patients.

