3.8.1 Neurologic Toxicity Assessment

1. Neurologic/CNS Toxicity will be graded according to the Common Toxicity Criteria for Adverse Events (CTCAE) version 4.03 (**Appendix B**).
2. Toxicity assessment will be made during treatment at weekly MD visits and at each follow up (1 month and 4 months after completion of radiation therapy, and every 3 months thereafter). A plus or minus 3 week window will be allowed for follow-up assessments.
3. Toxicity will be classified as immediate (within 24 hours of treatment), acute (within 4 months), or chronic (more than 4 months) based on timing after SRS.
4. Toxicities of any grade should be recorded by the radiation oncology staff on the study specific case report form at the prespecified assessment time points. All \geq grade 3 nervous system toxicity will be reported to the study principle investigator (PI).
5. Toxicities attributed to chemotherapy recorded by medical oncology staff will not be captured as study related AEs.
6. Attribution will initially be scored by the study investigators on the case report form and/or the physician seeing the patient in follow-up visit on a five point scale: 5=definitely caused by radiation treatment, 4= probably caused by radiation treatment, 3=possibly caused by radiation treatment, 2= probably not caused by radiation treatment, 1= not due to radiation treatment. Attribution will be reviewed by the PI and co-investigators. Any \geq grade 3 CNS toxicity with attribution ≥ 3 will be considered at DLT and will be reported to the DSMC. If a grade 3 CNS toxicity occurs after the patients is considered off study this will not be considered a DLT.
7. Any grade 5 toxicity will halt the study for review by the DSMC and IRB.
8. Maximal Tolerated Dose (MTD)
The MTD will be defined as the highest dose level where a grade 3 or greater with an attribution score of ≥ 3 develops in ≤ 2 of 6 patients in a dose group within 4 months of the treatment.
9. Laboratory values are not required for this protocol and will not be collected.

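### The primary-endpoint DLT includes late toxicity, but the MTD definition and primary analysis stop at 4 months; the plan does not say whether later DLTs count, and Section 5.3.1 gives no MTD estimate and no rate by dose

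*Combined protocol and SAP*

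**What the plan says.** Section 2.1.2 makes DLT a primary endpoint and defines it as "any acute or late CNS toxicity with grade greater than or equal to 3 with attribution score greater than or equal to 3". It sets no time limit. Section 3.8.1, item 3, puts the boundary between early and late as follows: "acute (within 4 months), or chronic (more than 4 months) based on timing after SRS". Item 6 of that section excludes grade 3 CNS events that arise once a patient is off study. Section 4.6 lists three ways to leave the study (death, whole brain radiation, patient request), and reaching month 4 is not one of them. A qualifying event at month 7 in a patient still on study is therefore a DLT. Appendix A schedules toxicity assessment at months 1 and 4 and then every 3 months to month 25.

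For the MTD, Section 3.8.1, item 8, takes the highest level at which qualifying events occur in no more than "2 of 6 patients in a dose group within 4 months of the treatment". Section 3.2 instead chooses each later dose "on the basis of all available data and the target highest acceptable toxicity level of 25% DLT". It says the MTD will be one of the six levels in Table 1, but names no estimator and no event window.

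Section 5.1.1 lists the MTD as the first primary endpoint and treatment-related neurologic toxicity as the second. The whole primary analysis, in Section 5.3.1, is one sentence: "The rate of toxicities at 4 months will be calculated with 95% confidence interval (CI". It does not state grade, attribution, denominator, interval method or dose level. The strata in Section 5.3.3 are intact lesion versus cavity and prior cranial radiation versus none. Dose level is not among them, and Section 5.3 has no analysis of late toxicity.

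**The concern.** The endpoint and its analysis cover different periods. A DLT at months 5 to 25 meets the primary-endpoint definition, yet it enters no toxicity analysis that Section 5.3 states, and it falls outside the MTD definition in Section 3.8.1. Section 3.2 could be read to admit it. Two statisticians following the text could feed different events into the dose model and name different MTDs from the same data.

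Late effects are central to this trial's question: Table 1 gives a late-effects BED for every dose level. What is at stake is whether the recommended level meets the 25% target on the trial's own DLT definition, or only on the part of it seen by month 4. A second gap compounds this. The trial exists to find a dose, but its stated primary analysis neither estimates that dose nor shows toxicity at each level.

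**Working it through.** **1. The plan's own figure.** 8 cohorts × 3 patients = 24, which agrees with Section 5.2. The documents give no power or operating characteristics to reproduce, and nothing below changes N.

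**2. One event, four sections.** Take a grade 3 CNS event, attribution 3, at month 7 in a patient still on study.

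| Section | Does it count? |
|---|---|
| 2.1.2 (DLT definition) | Yes |
| 3.2 (dose assignment) | Yes, if all available data is read literally |
| 3.8.1 item 8 (MTD definition) | No, later than 4 months |
| 5.3.1 (primary analysis) | No, later than 4 months |

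**3. Could such events be on record when doses are set?** Accrual waits for the 4-month evaluation of everyone already enrolled. With visits on schedule, the dose for cohort 8 is set no earlier than 7 × 4 = 28 months after the start; the ±3 week window can shift this. Scheduled follow-up ends at month 25, so surviving patients in early cohorts could have most or all of their late assessments on record by then.

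**4. What a rate without a dose breakdown can hide.** Section 5.3.1 does not say whether the rate is pooled. Suppose it is, with 3 events in 24 patients, all among 6 patients at one level. Exact (Clopper-Pearson) 95% intervals:

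- Pooled: 3/24 = 12.5%, CI 2.7-32.4%.
- That level: 3/6 = 50%, CI 11.8-88.2%.
- Remaining patients: 0/18.

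The pooled figure would be identical if the three events were spread over three levels.

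**5. What the 4-month window can hide.** Let a be the DLT probability by month 4, and b the probability of an observed on-study DLT later among patients without an early one. Then total = a + (1 − a)b. The documents give neither a nor b, so both are assumptions. The Section 3.8.1 rule is met with probability Σ C(6,k) p^k (1 − p)^(6 − k) over k = 0, 1, 2, with p = a if only 4-month events count and p = total if late events count too.

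| a | b | Total | Rule met, 4-month events | Rule met, all events |
|---|---|---|---|---|
| 5% | 20% | 24% | 0.998 | 0.846 |
| 10% | 5% | 14.5% | 0.984 | 0.957 |
| 10% | 10% | 19% | 0.984 | 0.913 |
| 10% | 20% | 0.10 + 0.90 × 0.20 = 28% | 0.984 | 0.780 |
| 15% | 20% | 32% | 0.953 | 0.706 |

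With a = 10%, the total passes 25% once b exceeds (0.25 − 0.10)/0.90 = 16.7%. These figures describe the count rule for six patients at one level. They are not operating characteristics of EWOC.

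**The case against.** The best defence is that the plan is less closed to late events than Sections 3.8.1 and 5.3.1 suggest. Section 3.2 bases doses on all available data, and the DLT it targets includes late events. The same section has documented DLTs reviewed again at each dose decision. Section 7.2.4 sends toxicities of grade 3 or more to the monitoring committee every 4 months and/or before each escalation, and Section 6.6 lets the investigator halt the study. This stands: a reader might infer that late DLTs can never affect the MTD, and the documents do not support that. What they leave unsettled is whether late DLTs do. Safety review also does not supply a rule for the model or the final estimate.

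A reader might also infer that the primary rate is planned as an average over all doses and so describes none of them. That reads a plan into silence. The Section 5.3.3 statement, "All enrolled patients will proceed through dose escalation as a single cohort", says only that escalation is not run separately by lesion type or prior radiation. Nor is the MTD itself pooled: Section 3.8.1 works within a dose group and Section 3.2 selects one level. Section 3.2 does say that an MTD will be estimated, so the gap is the missing method in Section 5.3, not a missing step. The word toxicities in Section 5.3.1 may well refer to the second primary endpoint, although it is tied to no grade or attribution.

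Two limits on size also stand. Survival may be short: one series cited in Section 1.0 had a median of 7.5 months from treatment. Death, whole brain radiation and withdrawal all end the period in which a grade 3 event can be a DLT, so the observable late share may be small. And exceeding 25% does not require late events, since the rule accepts 2/6 = 33% within 4 months. That is a further difference between Sections 3.2 and 3.8.1 to reconcile; it does not remove the mismatch in windows.

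**Conclusion.** The concern holds as a conflict between sections and a gap in the analysis plan. Sections 2.1.2, 3.2, 3.8.1 and 5.3.1 do not agree on whether a DLT after month 4 counts toward dose decisions or the final MTD. Section 5.3 gives no MTD estimator, no rate by dose and no late-toxicity analysis. These statements rest on the text alone.

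The size is conditional. Under the Section 3.8.1 rule, a level can be named the MTD while its acute-plus-late DLT rate is above 25%. By how much depends on a late share that the documents do not give: with an assumed 10% early rate, the total runs from 14.5% to 28% as the later rate goes from 5% to 20%. The contrast between 12.5% and 50% applies only if the primary rate is pooled. The point merits action because the first primary endpoint lacks a consistent, stated analysis, and the data needed are already scheduled for collection.

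**What to change.** 1. Reconcile Sections 2.1.2, 3.2, 3.8.1 and 5.3.1 so that they state the same thing about which DLTs enter the EWOC model at each decision and which enter the final MTD. Which events should drive escalation is for the investigators to decide; the request here is that the sections agree.
2. Replace Section 5.3.1 with:
   - the final model-based MTD estimate with its 95% credible interval;
   - the DLT proportion at each dose level with an exact 95% CI, using the Section 2.1.2 grade and attribution criteria;
   - a descriptive analysis of DLTs after month 4, as cumulative incidence with death as a competing event, by level where numbers allow, stating how patients who leave the study for whole brain radiation or at their own request are handled.
3. Report the final MTD based on 4-month DLTs next to the final MTD based on all on-study DLTs.

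N stays 24 and no visits are added. Items 2 and 3 need new analysis text and use data already scheduled. Item 1 edits the protocol, and would be a substantive amendment if it changes which events guide dose assignment. The drawbacks are wide per-level intervals (0/6 gives 0-45.9%; 2/6 gives 4.3-77.7%) and an all-DLT MTD that may be lower than the 4-month one.

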Stereotactic Radiosurgery, as defined by the American Society for Therapeutic Radiology and Oncology (ASTRO), the American Association of Neurological Surgeons (AANS), and the Congress of Neurological Surgeons (CNS), includes single dose SRS and well as HR delivered in 2-5 fractions over multiple days¹⁴⁻¹⁵. The majority of data supporting the use of SRS for the treatment of brain metastases has evaluated only single dose SRS and it is unclear whether the same results can be attributed to HR in 2-5 fractions. Brain metastasis amenable to single fraction SRS are typically defined as those measuring less than 3cm and producing less than 1cm of midline shift³. For brain metastasis not amenable to SRS, but for which focal brain radiation is indicated for boost or as salvage after WBRT or for avoidance of neurocognitive decline, HR provides an alternative treatment option. Current data describing the use and results of HR for the treatment of brain metastasis is limited to few retrospective series. Pater and colleagues from University of Cincinnati have demonstrated HR delivered to a dose of 30 Gy in 5 fractions to be effective and tolerable in a series of 34 patients, with a 6% (n=2) incidence of asymptomatic radiation necrosis and a 6 month actuarial local control rate of 68%¹⁶. A second series of 43 patients with metastatic breast cancer treated at Staten Island University Hospital utilized HR to a dose of 24 Gy delivered in 4 fractions, with a median survival from treatment of 7.5 months¹⁷. Recently, Wang et al. have reported on the use of HR in the setting of resected brain metastasis with resection cavities > 3cm and have demonstrated a local control rate of 80% at 6 months with the use of 24 Gy in 3 daily fraction¹⁸. With only a few series reported, the optimal dose and fractionation schedule is unknown.

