In our own experience at Emory¹⁹ with 47 patients receiving HR for both solid intact metastasis (22) and resection cavities (25), we have demonstrated 6 month and 1 year LC rates of 69% (CI 0.62-0.77) and 59% (CI 0.67 – 0.50), with 3 (6.4%) patients experiencing symptomatic radiation necrosis. On multivariate Cox-regression analysis, improved local control was associated with smaller planned target volume (PTV) volume (SS, $p=0.02$) and higher dose per fraction (NS, $p=0.06$). No significant association was found between LC and previous RT received, resection cavity vs. solid tumor, total dose, biological equivalent dose (BED) or single fraction equivalent dose (SFED). These results show HR is well tolerated in both new and recurrent, previously irradiated large intact or resected brain metastases. Significantly higher rates of local failure are observed with larger PTV volumes suggesting a need for dose escalation when using HR for large intracranial lesions.

We propose a prospective phase I trial for patients with solid brain metastasis greater than 3cm and less than 6 cm, who have either had no treatment or who are status post surgical resection. The purpose of this trial will be to determine the maximum tolerated dose for fractionated radiosurgery delivered in 5 fractions with a minimum of 2 and a maximum of 3 fractions being delivered per week. Results from this trial may form the basis of future trials evaluating the efficacy of fractionated radiosurgery regimens for local and distant control of brain metastasis and for directly comparing WBRT with FRS, for patients not amenable to single fraction SRS. Such a phase III study would answer the question about as to whether local irradiation is adequate treatment for patients with large brain metastasis.

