2.2.1 Local control: lack of progression of disease in resection cavity

2.2.2 Distant control: lack of progression of disease in surrounding brain

2.2.3 Overall survival: death from any cause

2.2.4 Long-term neurocognitive outcomes: using the Hopkins Verbal Learning Test–Revised (HVLT-R), Mini Mental Status Exam (MMSE) and Cognitive Functioning Subscale of the Medical Outcomes Scale (MOS).

2.2.5 Quality of life (QOL) outcomes: using the quality of life questionnaire for the Functional Assessment of Cancer Therapy-Brain (FACT-Br).

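### Sections 5.3.2.1 and 5.3.2.3 do not say how death is handled, so progression would probably be overstated and the cognitive and QOL slope intervals may be too narrow

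*Combined protocol and SAP*

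**What the plan says.** Section 5.3.2.1 of the combined protocol and SAP states: "The median time to local/distant brain progression will be calculated by Kaplan-Meier method with 95% CI". It continues: "For a given time point, say 4 month, the rate of local/distant progression will be calculated with 95%CI". No estimator is named for that rate.

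The endpoint is progression only. Section 2.2.1 reads "Local control: lack of progression of disease in resection cavity", and section 2.2.2 defines distant control in the same way for the surrounding brain. Death takes a patient off study (section 4.6.1). The plan does not say whether a death without progression is censored, counted as an event or treated as competing.

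Death does appear elsewhere among the secondary endpoints. Section 5.3.2.2 gives a Kaplan-Meier median for overall survival. Section 5.1.2 lists freedom from failure/progression-free survival, but section 5.3 gives it no analysis.

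For the cognitive and QOL scales, section 5.3.2.3 says: "Neurocognitive effect and QOL outcomes will be regressed over time using GEE model", with the population slope and a 95% CI. It names no working correlation, variance estimator, small-sample correction or handling of visits lost to death. Assessments are at baseline and months 1, 4, 7, 13, 19 and 25 (section 3.8.3). On size, section 5.2 says a "fixed sample size of 24 will be used".

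**The concern.** When a progression-only endpoint is analysed by Kaplan-Meier, deaths without progression are ordinarily censored. The estimate then describes a setting in which nobody dies first, and it exceeds the proportion of patients who do progress. In this population death may be more frequent than local failure, so the difference need not be trivial. Section 1.0 says the results may form the basis of later efficacy trials, and overstated failure rates would carry over into their planning.

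The GEE slope raises two separate problems. The usual sandwich variance is too small when there are few clusters, and here the late visits that weigh most on a slope to month 25 would rest on a handful of survivors. In addition, if patients who decline faster die sooner, the slope itself is biased toward less decline, and a better variance does not cure that.

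**Working it through.** **Plan's own figure.** Section 3.2: "This study will include 8 patient cohorts with 3 patients per cohort". 8 × 3 = 24, which agrees with section 5.2. The plan states no expected progression rate or precision for the secondary analyses, so there is nothing further to reproduce.

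**Inputs from section 1.0.** The institution's own series gives local control of 69% at 6 months and 59% at 1 year. One external series is reported "with a median survival from treatment of 7.5 months". Hazards are assumed independent and, within intervals, constant.

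- Local progression, months 0–6: λ₁ = −ln(0.69)/6 = 0.0618 per month
- Local progression, months 6–12: λ₂ = ln(0.69/0.59)/6 = 0.0261 per month
- Death: μ = ln 2/7.5 = 0.0924 per month

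**Progression.** With deaths censored, 1−KM = 1 − exp(−λt). Cumulative incidence = λ/(λ+μ) × [1 − exp(−(λ+μ)t)].

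- 4 months: 1 − exp(−0.247) = 21.9%, against 0.401 × [1 − exp(−0.617)] = 18.5%.
- 6 months: 31.0%, against 0.401 × [1 − exp(−0.926)] = 24.2%.
- 12 months, using both control rates: 1 − 0.59 = 41%. Alive and progression-free at month 6 is 0.69 × exp(−0.555) = 0.396. Cumulative incidence is 0.242 + 0.396 × [0.0261/0.1185] × [1 − exp(−0.711)] = 0.286, about 29%.

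Varying the assumed median survival from 6 to 18 months, with the same formulas:

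| Month | 1−KM | Cumulative incidence, median survival 6 / 7.5 / 12 / 18 months |
|---|---|---|
| 4 | 21.9% | 17.7 / 18.5 / 19.7 / 20.4% |
| 6 | 31.0% | 22.8 / 24.2 / 26.5 / 27.9% |
| 12 (both rates) | 41.0% | 26.5 / 28.6 / 32.5 / 35.0% |

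The gap at 4 months is therefore 4.2 down to 1.5 points, and at 12 months about 15 down to 6 points.

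*Median.* On the 6-month hazard the Kaplan-Meier median is ln 2/0.0618 = 11.2 months. Yet at most λ₁/(λ₁+μ) = 0.0618/0.1543 = 40% would ever progress locally, so the cumulative incidence never reaches one half. If instead λ₂ applies from month 6 onward, the Kaplan-Meier median is 12 + ln(0.59/0.50)/0.0261 = 18.3 months, and the ceiling is 0.242 + 0.396 × 0.220 = 33%.

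The document gives no distant progression rate. Assuming 30–50% at 6 months and the 7.5-month survival, the gap is 3–6 points at 4 months and 18–24 points at 12 months, the latter with the hazard held constant.

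**GEE slope.** Expected number alive is 24 × 2^(−t/7.5): 16.6, 12.6, 7.2, 4.1 and 2.4 at months 4, 7, 13, 19 and 25. At a 12-month median it is 19.0, 16.0, 11.3, 8.0 and 5.7.

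Trials of 24 patients were simulated at the protocol's visit times, 1,500 per setting, with visits stopping at death. The following are assumptions, not figures from the document: random intercept SD 1.0, residual SD 0.7, random slope SD 0, 0.03 or 0.06 per month, and independence or exchangeable working correlation. Coverage of a nominal 95% interval, with Monte Carlo error of about 1 point:

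| Setting | Uncorrected sandwich, normal reference | Mancl-DeRouen, t with 22 df |
|---|---|---|
| Median survival 7.5 months | 83.7–88.6% | 91.2–94.4% |
| Median survival 12 months | 88.9–91.9% | 92.9–95.5% |
| No deaths | 93.5–94.3% | 95.3–96.3% |

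Allowing for Monte Carlo error, the first row is roughly 83–89% against 90–94%. In all three rows death is unrelated to decline and the slope has almost no bias.

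If steeper decliners die sooner (hazard ratio exp(0.3) to exp(0.6) per SD of slope, 7.5-month median), the uncorrected interval covers about 65–83% and the corrected one about 76–90%, with bias toward less decline. With 12 patients, as could arise in the strata of section 5.3.3, the uncorrected interval covers about 78%.

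**The case against.** **A reader might infer that the secondary analyses ignore death altogether.** They do not. Overall survival is analysed and PFS is listed. The gap is confined to sections 5.3.2.1 and 5.3.2.3, plus the missing PFS analysis.

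**A reader might infer that the plan prescribes censoring at death.** It does not say so. Censoring is the natural reading of a progression-only endpoint, and the size of the overstatement is conditional on it.

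**A reader might take the 6-month hazard forward to month 12** and report 52% v 34%. The institutional series contradicts this: 59% control at 1 year is 41% failure, and using both rates the comparison is 41% v 29%.

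**Kaplan-Meier is not wrong for every question.** Under independence it estimates failure in the absence of death, and one of the earlier series cited in section 1.0 reports an actuarial control rate. This stands as a reason to keep it as a supplement, but it is not the probability that a treated patient progresses.

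**The difference at 4 months, the only time point the plan names, is small.** It is 1.5–4 points, against a half-width of about 1.96 × √(0.22 × 0.78/24) = 17 points. This stands. The case rests on later times and the median.

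**The inputs are borrowed.** The 7.5-month median comes from a breast cancer series at another dose and fractionation, whereas this trial takes mixed solid tumours with KPS of at least 70. The GEE standard deviations are assumed and the plan names no variance estimator. This stands too. At a 12-month median the shortfall from 95% is only about 3–6 points, so coverage far below 95% is not established.

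**Conclusion.** The point holds as a recommended improvement to the secondary analyses. On the natural reading, section 5.3.2.1 overstates the probability of progression: by about 3 points at 4 months, 7 at 6 and 12 at 12 for local progression, assuming 7.5-month median survival, independent hazards and the institution's own control rates. The direction does not depend on the survival assumption, but the size does. The median suffers most, because at that survival fewer than half of patients would ever progress locally. With longer survival (12 months or more on the 6-month hazard) half eventually would, and this part of the argument weakens.

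For section 5.3.2.3, an uncorrected interval would probably fall short of 95%, by roughly 6–12 points at a 7.5-month median and 3–6 points at 12 months. That is a small-sample variance problem. Bias arises only if death is related to decline, on which the document gives no information. It would be wrong to infer any effect on dose escalation or the MTD, since neither uses these analyses, and section 5.3.2.3 attaches no test or decision rule to the slope.

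**What to change.** **Section 5.3.2.1.** Estimate local, marginal and distant progression by cumulative incidence (Aalen-Johansen), with death without progression as a competing event. Report it with 95% CI at 4, 6 and 12 months in place of the median. Keep Kaplan-Meier as a supplement for comparison with earlier series, stating that deaths are censored there. Analyse the listed PFS endpoint by Kaplan-Meier with death as an event.

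**Section 5.3.2.3.** Name the working correlation, and use a small-sample corrected sandwich (such as Mancl-DeRouen) with a t reference, or a REML mixed model with Kenward-Roger degrees of freedom. Keep the slope to month 25, because section 2.2.4 asks for long-term outcomes, and report the slope to month 7 beside it, where about half the patients are expected to be alive. Restricting the analysis to month 7 alone would cut against that endpoint. Add a sensitivity analysis for death-related dropout, since the variance correction does not address it.

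**Cost.** A few sentences in the SAP and standard software. The slope intervals become wider, and the main progression estimates are less directly comparable with earlier Kaplan-Meier series.
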